	$\leq 2/6$ pts. peak ACT > 300 ≥ 3 pts. peak ACT < 200 (Cohort 2) $\leq 1/6$ pat with BARC 3 to 5 No SAE due to study drug In $\leq 1/6$ pat lab values preventing dose escalation such as LFT up by $\geq 2 \times$ from baseline; platelet count < 50,000; QTcF interval > 500 ms or > 60 ms change from baseline, based on ECGs; or study drug related vital sign changes that require stabilization of hemodynamics with positive inotropes	Any ACT > 350 BARC 3 to 5 Any AE/SAE due to study drug that requires switching patient to standard of care Lab values preventing dose continuation such as LFT up by $\geq 2 \times$ from baseline; platelet count < 50,000; QTcF interval > 500 ms or > 60 ms change from baseline, based on ECGs; or study drug related vital sign changes that require stabilization of hemodynamics with positive inotropes	$\geq 3/6$ pts. Peak ACT > 300 $\geq 2/6$ pat with BARC 3 to 5 $\geq 2/6$ SAEs due to study drug In $\geq 2/6$ pat lab value preventing dose escalation such as LFT up by $\geq 2 \times$ from baseline; platelet count < 50,000; QTcF interval > 500 ms or > 60 ms change from baseline, based on ECGs; or study drug related vital sign changes that require stabilization of hemodynamics with positive inotropes	$\leq 3/6$ pts. Peak ACT > 300 $\leq 1/6$ pat with BARC 3 to 5 No SAE due to study drug In $\leq 1/6$ pat lab values preventing dose escalation such as LFT up by $\geq 2 \times$ from baseline; platelet count < 50,000; QTcF interval > 500 ms or > 60 ms change from baseline, based on ECGs; or study drug related vital sign changes that require stabilization of hemodynamics with positive inotropes	$> 3/6$ pts. Peak ACT > 350 AND $> 2/6$ pat with BARC 3 to 5 OR $\geq 2/6$ SAEs due to study drug In $\geq 3/6$ pat lab values preventing dose escalation such as LFT up by $\geq 2 \times$ from baseline; platelet count < 50,000; QTcF interval > 500 ms or > 60 ms change from baseline, based on ECGs; or study drug related vital sign changes that require stabilization of hemodynamics with positive inotropes
Abbreviations: AE, adverse event; ACT, activated clotting time; BARC, Bleeding Academic Research Consortium; ECG, electrocardiogram; LFT, liver function test; pat, patient; QTcF, QT interval corrected by Fridericia's formula; SAE, serious AE.					

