
• Bolus dosing All patients will receive 0.75 mg/kg as an IV bolus dose, followed immediately by 1.6 mg/kg/hr*4h IV for the duration of the PCI. Five minutes after the bolus dose, ACT should be performed and an additional bolus of 0.3 mg/kg IV may be given if needed (i.e., ACT <200 sec).									

• Dosing during infusion period 10 minutes after initiation of 1.6 mg/kg/hr IV for the duration of the PCI, or 5 minutes after additional bolus if it is given, additional ACT can be monitored, and IP infusion rate can be adjusted. An incremental 10% additional infusion rate can be titrated up until ACT >200 sec. If ACT >300 sec during that period of time, IP infusion can be stopped for 5 minutes, and/or the rate of infusion can be adjusted until ACT maintains between 200 sec and 300 sec. Duration of IP infusion can be 4 hours +-30 minutes in order to accommodate potential infusion rate adjustments.									

Reference Therapy:	None
Treatment Duration:	Treatment in preparation for PCI, during PCI, and until approximately 4 hours after enrollment. Patients will receive MT1002 IV followed by MT1002 infusion for 4 hours. This regimen was found safe and well tolerated in Phase 1. MT1002 will be initiated as close to the start of PCI as possible. PCI can start after MT1002 initiation as soon as ACT is confirmed to be ≥ 200 sec or within 30 min after MT1002 starts, whichever occurs first. Patients will be discharged from the hospital when they are stable, as defined by the Investigator's judgment. Patients will be followed for 30 days from study drug dosing.
Key Efficacy:	The numbers of patients who achieve ACT target 200 to 300 sec, and measurement of Platelet Aggregation (PA)
Key Safety:	General safety (including vital signs, physical examination, electrocardiogram [ECG], laboratory assessments), AEs, MACE within 30 days, and major bleeding events
Pharmacokinetics:	PK levels of MT1002
Pharmacodynamics:	ACT, aPTT, PT, TT, FIB, INR
Other Assessments:	Thrombolysis in myocardial infarction (TIMI) flow assessments; creatine kinase (CK)-MB, and troponin I (troponin T can be measured if the local site does not have the troponin I test)

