5.2 Study Endpoints

5.2.1 Co-Primary Endpoints

The co-primary endpoints of this study are:

- The number of patients with target ACT (200 to 300 seconds [sec]) achieved on MT1002 (with no switch to standard of care) prior to and during PCI and PCI success. PCI success is defined as achievement of < 30% residual diameter stenosis of all treated lesions as assessed by visual inspection or Quantitative Coronary Analysis (QCA), without an in-hospital major adverse cardiac event (death, myocardial infarction [MI], or repeat coronary revascularization of the target lesion)
- AE of interest: bleeding events major (Bleeding Academic Research Consortium [BARC] Type 3–5)

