6 INVESTIGATIONAL PLAN

6.1 Description of Overall Study Design and Plan

This is an open-label, sequential-dose escalation/de-escalation trial testing 3 dose levels of MT1002 in patients undergoing PCI due to ACS with NSTEMI. Three doses of MT1002 will be sequentially tested in cohorts of 6 patients each to achieve target ACT.

Pre-specified dose escalation/de-escalation/stopping/continuation rules for the patient cohorts are shown in Table 1 below.

Table 1 Rules for Dose Escalation/De-Escalation/Stopping/Continuation

Continue to next higher dose group if:	Stop study drug infusion temporarily in an individual patient if:	Stop dose group and de-escalate according to protocol if:	Continue the same dose in the next patient cohort (to get more data for initial dose) if:	Stop the study if:
$\leq 2/6$ pat peak ACT > 300	Any ACT > 350 or < 180	$\geq 3/6$ pat peak ACT > 300	$\leq 3/6$ pat peak ACT > 300	> 3/6 pat peak ACT > 350
≥ 3 pts. peak ACT < 200 (Cohort 2)				AND
$\leq 1/6$ pat with BARC 3 to 5	BARC 3 to 5	$\geq 2/6$ pat with BARC 3 to 5	$\leq 1/6$ pat with BARC 3 to 5	> 2/6 pat with BARC 3 to 5
				OR
No SAE due to study drug	Any AE/SAE due to study drug that requires switching patient to standard of care	$\geq 2/6$ SAEs due to study drug	No SAE due to study drug	$\geq 2/6$ SAEs due to study drug

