Follow-up: At completion of PCI, subjects will be continued on IV MT1002 for 4 hours from infusion start. All patients will stay on clopidogrel 75 mg/day. If the local clinical guidance recommends use of Ticagrelor or Prasugrel, the recommended maintenance doses will be: Ticagrelor 90 mg twice daily or Prasugrel 5-10 mg daily and aspirin 75-100 mg/day (according to local countries clinical practice guidance) and be followed up for 30 days. Longer-term follow-on treatment will be done according to local treatment guidelines outside of this protocol.

Rescue: Patients who fail to achieve an ACT target of 200 to 300 sec with MT1002 (within 30 minutes after MT1002 infusion initiation) will be switched to standard of care (unfractionated heparin [UFH] or bivalirudin) and discontinued from the study drug.

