All patients will receive 0.75 mg/kg as an IV bolus dose, followed immediately by 1.6 mg/kg/hr*4h IV for the duration of the PCI. Five minutes after the bolus dose, ACT should be performed and an additional bolus of 0.3 mg/kg IV may be given if needed (i.e., ACT <200 sec).

- Dosing during infusion period

10 minutes after initiation of 1.6 mg/kg/hr IV for the duration of the PCI, or 5 minutes after additional bolus if it is given, additional ACT can be monitored, and IP infusion rate can be adjusted. An incremental 10% additional infusion rate can be titrated up until ACT >200 sec. If ACT >300 sec during that period of time, IP infusion can be stopped for 5 minutes, and/or the rate of infusion can be adjusted until ACT maintains between 200 sec and 300 sec. Duration of IP infusion can be 4 hours +/-30 minutes in order to accommodate potential infusion rate adjustments.

Table 3 Planned Dose Regimen of MT1002 for Injection and Expected ACT and aPTT Values

Sequence	N	MT1002: Initial loading dose and maintenance dose	Expected peak ACT based on Phase 1 results in healthy volunteers	Expected peak aPTT based on Phase 1 results in healthy volunteers	Expected ACT in 5 min after MT1002 start	Expected aPTT in 5 min after MT1002 start	Expected ACT in 30 min after MT1002 start	Expected aPTT in 30 min after MT1002 start
First dose cohort	6	0.90 mg/kg + 1.8 mg/kg/h*4h	234.3±26.1 sec – at 4 hours	74.4±6.2 sec – at 4 hours	209.7±19.2	63±4.8	212.3±29.5	65.6±7.5
Second cohort if dose escalated	6	1.2 mg/kg + 2.3mg/kg/h*4h	253.8±9.6 sec – at 2 hours	83.6±5.4 sec – at 4 hours	234.3±6.9	74.5±7.3	240.3±4.1	78.3±9
Second cohort if dose de-escalated	6	0.60 mg/kg + 1.2 mg/kg/h*4h	221.7±11.1 sec – at 2 hours	65.9±2.5 sec – at 4 hours	194.5±28.6	56.5±7.4	216.2±15.7	60.6±4.4
Third expansion cohort	6-8	0.75 mg/kg + 1.6 mg/kg/h*4h based on results from initial 2 cohorts	220.7 sec at 4 hours	67.7 sec at 4 hours	217.5	66.5	216.5	66.1

Abbreviations: ACT, activated clotting time; aPTT, activated partial thromboplastin time; h, hours; min, minutes; N, number of patients; sec, seconds; Tbd, to be determined.

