Aspirin, clopidogrel (or Ticagrelor or Prasugrel), bivalirudin as a rescue therapy, and glycoprotein IIb/IIIa inhibitor as bail out for PCI is standard practice and not exclusive to this study. Therefore, these agents will be supplied by the hospital pharmacy or other local qualified pharmacy source as part of the local standard of care.

Concomitant anticoagulant therapy:

All patients should receive evidence-based medications for coronary artery disease (e.g., beta-blockers, ACE-inhibitors, statins, diabetic medications, etc.) as recommended in practice guidelines and/or per local standard of care. Concomitant medications through Day 30 will be recorded in the source documents and eCRF. In addition:

- Heparin is not permitted from enrollment through 7 hours post-MT1002 infusion completion except for the following situations (per local standard of care):
 - After enrollment, patients who fail to achieve ACT target of 200 to 300 sec with MT1002 (within 30 minutes after MT1002 infusion initiation) can be switched to UFH as a standard of care. UFH cannot be administered simultaneously with MT1002; MT1002 treatment should be discontinued 30 minutes before switching to UFH (dosing per local standard of care).
 - In the case of intracoronary or stent thrombosis during the procedure or within 24 hours after the procedure, heparin may be administered as a bail out therapy if it is deemed that inadequate anticoagulation has been achieved with MT1002 based on clinical or angiographic findings.
Monitoring of ACT levels and administration and dosing of UFH should be performed per local standard of care and should be continued to maintain a therapeutic level of anticoagulation.
 - In patients undergoing emergent or urgent open-heart surgery after the PCI
 - In patients undergoing urgent device placement that requires continuous anticoagulation (e.g., intra-aortic balloon pump)
 - For routine flushing of catheters and IV lines, including radial or femoral access catheters.
- Heparin is permitted after 4 hours post sheath removal (per local standard of care).

The concomitant administration of proton pump inhibitors is strongly recommended in patients without clinical contraindications for those agents, to reduce the risk of gastrointestinal bleeding. Proton pump inhibitors that do not interact with CYP2C19 (lansoprazole, pantoprazole, etc.) should be used.

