- ⁱ MT1002 will be initiated as close to the start of PCI as possible. MT1002 should be initiated during diagnostics angiography when indication for PCI is confirmed, provided the early PCI is indicated right after the coronary angiography. PCI can start after MT1002 initiation as soon as ACT is confirmed to be ≥ 200 sec or within 30 min after start of MT1002, whichever occurs first.
- ^j Pharmacokinetic samples will be taken at Day 1 pre-dose; at 5 (± 1) min after MT1002 intravenous injection; and 0.5 (± 5 min), 4 (-5 to 10 mins, 5-10 min before the infusion completion), 6 (± 15 min), 8 (± 15 min), and 24 (± 15 min) hours post-dose initiation.

- ^k ACT, aPTT, and PT, TT, FIB, INR will be taken at Screening; on Day 1 pre-dose; at 5 (± 1) min after MT1002 intravenous injection; and 0.5 (± 5 min), 4 (-5 to 10 mins, 5-10 min before the infusion completion), 6 (± 5 min), 8 (± 15 min), and 24 (± 15 min) hours post-dose initiation.
- l Between screening and Pre-PCI within 48 hours, Vital signs, 12-lead ECG, CK-MB, cardiac troponin I (troponin T can be measured if the local site does not have the troponin I test), ACT, aPTT, PT, TT, FIB, INR, PA (PFA100 or PFA 200), Hematocrit, hemoglobin, platelet count, RBC and WBC counts take once; screening and Pre-PCI beyond 48 hours, should take twice before PCI.

Table 5 Time Points for Platelet Aggregation, Cardiac Biomarkers, Coagulogram, and Pharmacokinetics

Time points/ blood tests	Screening	Day1 pre-dose	5 min (± 1 min) post-dose initiation	0.5 h (± 5 min) post-dose initiation	4h (-5 to 10 min) post-dose initiation, 5-10 min before the infusion completion)	6h (± 15 min) post-dose initiation	8 h (± 15 min) post-dose initiation	24 h (± 15 min) post-dose initiation
PA	X		X	X	X	X	X	X
Cardiac biomarkers ^a	X	X		X	X	X	X	X
ACT, aPTT, PT, TT, FIB, INR	X	X	X	X	X	X	X	X
PK		X	X	X	X	X	X	X

Abbreviations: ACT, activated clotting time; aPTT, activated partial thromboplastin time; h, hours; PA, platelet aggregation; min, minutes; PK, pharmacokinetics; PT, prothrombin time; TT, Thrombin time; FIB, Fibrinogen; INR, International Normalized Ratio.

^a Creatine kinase-MB, cardiac troponin I (troponin T can be measured if the local site does not have the troponin I test).

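### Section 6.1 Table 1 pauses the MT1002 infusion when ACT is below 180 sec; the synopsis copy of that rule does not, and the Cohort 3 guide allows more drug at the same reading

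*Combined protocol and SAP*

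**What the plan says.** - **Section 6.1, Table 1**, column for temporarily stopping the infusion in an individual patient: "Any ACT > 350 or < 180". The cell is not limited to any cohort.
- **Synopsis**, same column of the same table: "Any ACT > 350 BARC 3 to 5". The text goes straight from the upper ACT limit to the bleeding criterion, with no lower limit.
- **Section 8.2, Cohort 3 guide** (repeated in the synopsis): five minutes after the bolus, an "additional bolus of 0.3 mg/kg IV may be given if needed (i.e., ACT <200 sec"). From 10 minutes after the infusion starts, or 5 minutes after an extra bolus: "An incremental 10% additional infusion rate can be titrated up until ACT >200 sec".
- **Table 4, footnote k**: ACT is scheduled "at 5 (± 1) min after MT1002 intravenous injection", among other times.
- **Section 6.1, rescue**: "Patients who fail to achieve an ACT target of 200 to 300 sec with MT1002 (within 30 minutes after MT1002 infusion initiation") are switched to heparin or bivalirudin and come off study drug.
- **Section 8.5.1**: "MT1002 treatment should be discontinued 30 minutes before switching to UFH". A similar interval of at least 30 minutes applies before bivalirudin.
- **Section 5.2.1**, first co-primary endpoint: target ACT "achieved on MT1002 (with no switch to standard of care) prior to and during PCI", together with PCI success.

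**The concern.** The target is 200-300 sec, so a reading below 180 sec means too little anticoagulation. Section 4.2.2 describes MT1002 as rapidly eliminated, so pausing it lowers ACT further. Section 8.2 allows PCI to begin once ACT reaches 200 sec or within 30 minutes of starting MT1002, whichever comes first. A patient paused at the 5-minute reading could therefore enter PCI off drug and under-anticoagulated.

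The pause also works against the co-primary endpoint. For the 0.60 mg/kg regimen, Table 3 expects mean ACT to rise from 194.5 sec at 5 minutes to 216.2 sec at 30 minutes with the infusion running. Stopping at 5 minutes takes away the infusion that is expected to bring the patient into range.

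The two copies of the table give a site opposite answers to the same reading, and no current text says which prevails. Section 8.2 describes a 5-minute pause for ACT above 300 sec, but nothing states when to restart after a pause for low ACT. Recovery of ACT cannot be the trigger, because ACT will not recover with the drug off.

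**Working it through.** **1. The rules side by side**

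| ACT reading | Section 6.1 Table 1 | Synopsis table | Section 8.2 (Cohort 3 only) |
|---|---|---|---|
| Above 350 | Pause | Pause | Pause and/or adjust rate (above 300) |
| 180 to 199 | No pause | No pause | Optional bolus; optional rate increase |
| Below 180 | **Pause** | **No pause** | **Optional bolus; optional rate increase** |

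The copies disagree only below 180 sec. In Cohort 2 (taken as the de-escalated 0.60 mg/kg regimen) there is no titration guide, so the conflict is pause against no pause. In Cohort 3 the direct clash is with the 10% rate increases, since an infusion cannot be both paused and raised. Table 1 does not forbid a bolus while the infusion is paused.

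**2. How often ACT would fall below 180 sec, healthy-volunteer values**

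Inputs are the means and SDs in Table 3; normality is assumed. P(ACT < c) = Φ((c − mean)/SD).

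- Cohort 2, 5 min, 194.5 ± 28.6: z = (180 − 194.5)/28.6 = −0.507, so P = 0.306. At least one of 6: 1 − (1 − 0.306)^6 = 0.89.
- Cohort 2, 30 min, 216.2 ± 15.7: for 180, z = −2.31, P = 0.011; for 200, z = −1.03, P = 0.151.
- P(below 180 at 5 min and at least 200 at 30 min) ≥ 0.306 − 0.151 = 0.155, whatever the correlation between the readings.
- Cohort 3, 5 min, mean 217.5. Table 3 gives no SD, so the 5-minute SDs of the other regimens are assumed: 6.9, 19.2 and 28.6 give z = −5.43, −1.95 and −1.31, and P below 0.1%, 2.5% and 9.5%.

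**3. Check of that model against Cohort 1**

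The version 6.0 entry reports that 3 of 6 Cohort 1 patients (0.90 mg/kg) had a 5-minute ACT above 300 sec. Table 3 expects 209.7 ± 19.2: z = (300 − 209.7)/19.2 = 4.70, so P(> 300) is about 1.3 × 10⁻⁶ per patient. The unscaled model does not describe these patients.

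**4. Scaling to fit Cohort 1**

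Multiply mean and SD by k and use the same k for every regimen (an assumption).

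| k | P(at least 3 of 6 above 300), Cohort 1 | P(< 180 at 5 min), Cohort 2 | P(< 180 at 5 min), Cohort 3, SD 28.6 × k |
|---|---|---|---|
| 1.0 | effectively 0 | 31% | 9.5% |
| 1.1 | 3 × 10⁻⁹ | 14% | 3.0% |
| 1.2 | 1 × 10⁻⁴ | 6% | 0.9% |
| 1.31 | 0.05 | 2.3% | 0.3% |
| 1.43 | 0.66 | 0.8% | under 0.1% |

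At k = 1.31 the Cohort 1 mean is 274.7 and the SD 25.2, so z = (300 − 274.7)/25.2 = 1.01, P(> 300) = 0.157, and P(at least 3 of 6) = 0.05. For Cohort 2 the mean is 254.8 and the SD 37.5: z = (180 − 254.8)/37.5 = −2.00, P = 0.023. The value 1.43 is 300/209.7, which puts the Cohort 1 mean at 300. With the Cohort 2 SD left at 28.6 there, P falls to 0.03%.

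**The case against.** The strongest defence is that the lower limit is an early step towards rescue. A switch to heparin or bivalirudin needs about 30 minutes off MT1002, so stopping early at a clearly low ACT could be deliberate. The word temporarily in the column heading does not rule this out, because the same column lists adverse events that require a switch to standard of care. That much stands. But rescue is judged against a 30-minute limit and means discontinuation, whereas Table 1 covers any ACT, including the 5-minute one, and mentions no switch for low readings. The synopsis would also still disagree.

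A second defence is that the version 6.0 entry shows the limit was meant to be removed or made resumable. Its wording on this rule is ambiguous, and a change log does not govern current text. The point does not rely on it.

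A third is that the Section 8.2 steps are optional and apply to Cohort 3 only. This is correct and limits the conflict as set out above.

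Two stronger readings are tempting and not supported:

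- **That about a third of Cohort 2 would be wrongly paused.** The 31%, 89% and 15.5% figures are arithmetically right, but they come from a model that Cohort 1 contradicts. The scalings of 1.1 and 1.2 fail the same check.
- **That the pause would inflate the count that sends the trial to Cohort 3.** Section 6.1 counts patients with at least one ACT below 200 sec. A patient paused for a reading below 180 is already counted, so the pause adds nobody under that definition. Only under the peak-ACT wording inside Table 1 could a pause matter, by holding a patient's peak below 200.

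**Conclusion.** The point holds and should be fixed. Two copies of one patient-level rule disagree for ACT below 180 sec. The version in Section 6.1, followed as written, withdraws the anticoagulant from an under-anticoagulated patient around PCI. In Cohort 3 it also contradicts the permitted rate increases.

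The frequency is uncertain: about 31% of Cohort 2 patients at 5 minutes on unscaled healthy-volunteer values, and about 2% or less on scalings compatible with Cohort 1. The lower figure is better supported, but it rests on normality, on a common multiplier across regimens, and on six patients. It also treats the Cohort 1 result as an upward shift; a wider spread between patients would not make low readings rarer in the same way. The conclusion depends on none of these figures. It follows from the text alone.

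**What to change.** 1. In Section 6.1 Table 1, delete the below-180 limit so that the cell matches the synopsis. The stops for ACT above 350 sec, BARC 3-5 bleeding, adverse events and laboratory values stay.
2. Add a line referring low ACT to the Section 8.2 dose adjustment guide in Cohort 3 and to the 30-minute rescue rule in all cohorts.
3. State that a patient outside Cohort 3 whose ACT falls below target after 30 minutes continues MT1002 unless switched to standard of care under Section 8.5.1. Deletion alone would leave this patient without a rule, because rescue covers only failure to reach target within 30 minutes.

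The cost is amendment wording and a short memo to sites. No extra procedures, data fields or patients are needed.

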Version 6.0	
Revised dose escalation/de-escalation/stopping /continuation rules based on end of Cohort 1 SMG safety review and recommendation 23Mar2023:
 
 Added “Continue to next higher dose group if 3 or more patients show peak ACT <200 sec in Cohort 2” to avoid inadequate treatment in cohort 2. Modified “Stop study drug infusion in an individual patient only temporarily and eliminate conditions if ACT <180.” The specific dosing adjustment guideline provided, therefore study drug infusion can be resumed to ACT at target level. Modified the criteria in Stop the study if: both more than 3/6 ACT >350 sec and more than 2/6 patients experience bleeding events with BARC 3-5. Both ACT as anti-coagulation level biomarker and actual significant bleeding events with BARC 3-5 are needed to justify study to be stopped due to significant risk of bleeding. 
Proposed new dosing regimen for cohort 3 at 0.75 mg/kg + 1.6 mg/kg/h*4h and dose adjustment guideline for cohort 3 dosing regimen per SMG’s recommendation based on the following findings in Cohort 1 and PK/PD modeling results from Phase I study:
 
 MT1002 was safe and well-tolerated in all 6 patients enrolled in the 0.90 mg/kg+1.8mg/kg/h*4h cohort of the study. None of the patients who received MT1002 experienced serious adverse events, major bleeding events or major adverse cardiovascular events. At 0.90 mg/kg+1.8mg/kg/h*4h dose-level, MT1002 achieved targeted ACT level resulting in successful PCI in all 6 patients. 3 patients had one peak ACT >300 after bolus injection at 5 minute, indicated the bolus dosing at 0.9 mg/kg can be reduced. 0.75 mg/kg is recommended by SMG if 0.6 mg/kg shows inadequate anti-coagulate effect. Only 1 patient had one peak ACT >300 at 30 minutes during infusion period, indicated 	16-Apr-2023
-------------	--	-------------

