Planned Sample Size:	
A total of up to 18 patients on MT1002 (3 cohorts of 6 patients) will be enrolled. Approximately 30 patients will need to be screened. The number of patients screened is based on a screen failure rate of 40%.

Investigational Therapy:	Monotherapy of MT1002, 3 doses via intravenous (IV) + infusion:								
	Sequence	N	MT1002: Initial loading dose and maintenance dose	Expected peak ACT based on Phase 1 results in healthy volunteers	Expected peak aPTT based on Phase 1 results in healthy volunteers	Expected ACT in 5 min after MT1002 start	Expected aPTT in 5 min after MT100 2 start	Expected ACT in 30 min after MT1002 start	Expected aPTT in 30 min after MT100 2 start
	First dose cohort	6	0.90 mg/kg + 1.8 mg/kg/h* 4h	234.3±26.1 sec – at 4 hours	74.4±6.2 sec – at 4 hours	209.7±19. 2	63±4.8	212.3±29. 5	65.6±7. 5
	Second cohort if dose escalate	6	1.2 mg/kg + 2.3mg/kg/h* 4h	253.8±9.6 sec – at 2 hours	83.6±5.4 sec – at 4 hours	234.3±6.9	74.5±7. 3	240.3±4. 1	78.3±9.
	Second cohort if dose de-escalated	3 - 6	0.60 mg/kg + 1.2 mg/kg/h* 4h	221.7±11.1 sec – at 2 hours	65.9±2.5 sec – at 4 hours	194.5±28. 6	56.5±7. 4	216.2±15. 7	60.6±4. 4
	Third expansion cohort	6 - 8	0.75 mg/kg + 1.6 mg/kg/h* 4h based on results from initial cohort(s)	220.7 sec at 4 hours	67.7 sec at 4 hours	217.5	66.5	216.5	66.1
	Abbreviations: ACT, activated clotting time; aPTT, activated partial thromboplastin time; h, hours; min, minutes; N, number of patients; sec, seconds; Tbd, to be determined.								
The goal is to achieve a target ACT of 200 to 300 sec (within 30 minutes after infusion initiation) during the continuous infusion period of MT1002.									
MT1002 should be started as close to the start of PCI as possible. MT1002 should be initiated during diagnostics angiography when indication for PCI is confirmed, provided the early PCI is indicated right after the coronary angiography.									
Patients who are enrolled but do not undergo PCI (e.g., because of PCI contraindication revealed after coronary angiography or due to exclusion criteria) will be replaced for the study. However, the patients will be evaluated as safety population.									
Dose adjustment guideline for cohort 3 dosing regimen, all adjustment will be documented in the patient’s source document in detail:									

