14.1 Determination of Sample Size

Based on clinical experience, a total of up to 18 patients will be enrolled to achieve the study objectives in this study. Approximately 30 patients will need to be screened. The number of patients screened is based on a screen failure rate of 40%.

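### Table 1's dose-decision columns overlap, leave a gap and state no precedence, and the printed cohort sizes fit neither its sixths nor the stated maximum of 18

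*Combined protocol and SAP*

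**What the plan says.** Table 1 in Section 6.1, with the same cohort-level thresholds in the synopsis copy, has four cohort-level columns: escalate, stop the dose group and de-escalate, continue the same dose, and stop the study. (A fifth column concerns infusion in an individual patient and is not at issue here.)

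- **Peak ACT above 300 seconds.** The de-escalate column reads "\geq 3/6$ pat peak ACT > 300" and the same-dose column reads "\leq 3/6$ pat peak ACT > 300" (the signs are ≥ and ≤). The escalate column allows at most 2/6.
- **SAEs.** "\geq 2/6$ SAEs due to study drug" stands in both the de-escalate and the stop-study columns. The escalate and same-dose columns both require that there be none.
- **Laboratory, ECG and vital-sign values.** De-escalate is met from 2/6 and stop-study from 3/6.

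The version 6.0 entry in the amendment log reports from Cohort 1 (six patients) that "3 patients had one peak ACT >300 after bolus injection at 5 minute", and that one patient had a value above 300 at 30 minutes.

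On size, the synopsis states "A total of up to 18 patients on MT1002 (3 cohorts of 6 patients) will be enrolled", and Section 14.1 repeats that "a total of up to 18 patients will be enrolled to achieve the study objectives in this study" and adds "Approximately 30 patients will need to be screened", from a 40% screen failure rate. The synopsis dose table gives 3 to 6 patients for the second cohort if de-escalated, where Table 3 in Section 8.2 gives 6. Both tables give 6 to 8 for the row labelled "Third expansion cohort" in the synopsis.

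Sections 6.1 and 8.3.1 leave each decision to the Study Management Group (SMG), which weighs safety, efficacy and drug concentration alongside these criteria.

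**The concern.** The primary objective (Section 5.1.1) is to find a safe and well tolerated dose. All analyses in Section 14 are descriptive, so Table 1 is the main stated route from data to a dose decision, and Section 6.2 relies on it to protect patients. A rule set of this kind has to give one answer for every possible result. Here one result meets two columns that point in different directions, some results meet two columns of different severity, and one result meets none. No precedence is stated.

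In those cells the outcome rests on judgement made after open-label data have been seen. The group making it includes sponsor representatives as well as an independent cardiologist, under a charter still to be established (Section 14.8). A reader of the final report could not tell whether such a decision followed the pre-specified rules. The mismatch between sixths and the permitted cohort sizes creates further undefined cells, and the printed sizes can exceed the stated maximum.

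**Working it through.** **Reading used.** AND and OR are printed only in the stop-study column. I take the rows as all required in the escalate and same-dose columns, and as alternatives in the de-escalate column. The stop-study column is read as printed, with its laboratory row as a further alternative.

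**1. The plan's own figures.** 3 cohorts × 6 = 18. Screened: 18 / (1 − 0.40) = 30. Both reproduce.

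**2. Columns met with six patients**

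| Result (other rows clean) | Columns met |
|---|---|
| 0–2 with peak ACT >300 | escalate, same dose |
| exactly 3 with peak ACT >300 | de-escalate, same dose |
| 4–6 with peak ACT >300 | de-escalate |
| exactly 1 drug-related SAE | none |
| 2 or more drug-related SAEs | de-escalate, stop study |
| 2 with laboratory/ECG/vital-sign values | de-escalate |
| 3 or more with such values | de-escalate, stop study |

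The single-SAE row meets no column because "none" fails and 2/6 is not reached.

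**3. Other cohort sizes**

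- n = 8: 2/8 = 0.25 lies between 1/6 = 0.167 and 2/6 = 0.333. Two patients with BARC 3–5 bleeding therefore meet no column if the threshold is a fraction, but meet de-escalate if it is a count of 2.
- n = 3 (synopsis only): 1/3 = 2/6. One drug-related SAE meets both de-escalate and stop-study as a fraction, but no column as a count.
- The SAE threshold is worded as a number of SAEs over six, beside rows that count patients.

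**4. Totals.** The printed sizes give from 6 + 3 + 6 = 15 to 6 + 6 + 8 = 20. Twenty enrolled would need 20 / 0.60 = 33.3, so 34 screened.

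**5. How often the cells might arise (n = 6).** The documents give no rates. I assume a probability p of peak ACT >300 of 0.3 to 0.5, a probability q of a drug-related SAE of 0.05 to 0.20, one SAE per affected patient, and independence.

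- Exactly 3 of 6 on ACT: 20 p³(1 − p)³ = 0.185 at p = 0.3 and 0.313 at p = 0.5. The same-dose column also needs no SAE: (1 − q)⁶ = 0.735 at q = 0.05 and 0.262 at q = 0.20. Products: 0.185 × 0.262 = 0.05 to 0.313 × 0.735 = 0.23.
- Exactly one SAE: 6q(1 − q)⁵ = 0.232 at q = 0.05 and 0.393 at q = 0.20. No column applies only if at most 2 of 6 exceed 300, with probability 0.744 at p = 0.3 and 0.344 at p = 0.5. Products: 0.232 × 0.344 = 0.08 to 0.393 × 0.744 = 0.29. The single-SAE probability peaks between those ends, at q = 1/6 (0.402), where the product with 0.744 is 0.30.

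Requiring the BARC and laboratory rows to be clean as well lowers both ranges.

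**The case against.** The strongest reply is that the table is guidance: the SMG decides in every case, with wider data and an independent cardiologist. That stands, and it answers the stronger reading a reader might take, that the same data dictate opposite decisions. They do not. But discretion to apply criteria does not reconcile criteria that disagree.

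Other points have force:

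- **Not every overlap is a conflict of direction.** That every escalate result also meets same-dose is permissive, since that column exists to gather more data. De-escalate and stop-study both halt the dose group and differ in severity, so they need a precedence line. Only the 3/6 ACT cell sets de-escalation against continuing.
- **Cohort 1.** A reader might infer that it landed exactly on the contradictory cell. The log does not say whether the patient above 300 at 30 minutes was one of the three at 5 minutes. The count was 3/6 or 4/6, and at 4/6 only de-escalate applies.
- **What is still live.** The Cohort 1 decision has been taken, the same-dose column refers to the initial dose, and the step from Cohort 2 to Cohort 3 has its own trigger in Section 6.1. This lowers the practical weight of the 3/6 cell. It does not touch the SAE cells, which apply to any cohort.
- **The reading of the rows.** If every row of the de-escalate column had to be met, the 3/6 conflict would vanish, but 4/6 above 300 with nothing else would then meet no column. The log explains the one printed AND as a deliberate change, which favours alternatives elsewhere.
- **The cap.** Some printed sizes respect 18 (6 + 6 + 6, or by the synopsis 6 + 4 + 8). The documents do not plan 20 patients; they permit it.

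**Conclusion.** The point holds as an internal contradiction in the decision rules and the stated maximum. With cohorts of six, exactly 3/6 above 300 meets both de-escalate and same-dose. Two or more drug-related SAEs, or three or more patients with laboratory, ECG or vital-sign values, meet both de-escalate and stop-study. A single drug-related SAE with other rows within limits meets nothing. These findings rest on the row-joining stated above but on no assumed rates. Cohort 1 was at or above the conflicting boundary; the documents do not show which.

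The frequencies, about 5–23% for the conflict and 8–29% for the gap at the ends of the assumed ranges, are illustrations. A reader might use the single-row figures instead (19–31% and 23–39%), but these ignore the other rows that must hold at the same time. The SAE range has no anchor: the documents report no SAEs in 30 Phase 1 subjects or in the six patients of Cohort 1. With an SAE rate below 5% the gap shrinks and the 3/6 conflict moves towards its single-row figure.

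The size discrepancy is 2 patients enrolled (20 against 18) and 4 screened (34 against about 30). It changes no analysis, but it contradicts a stated maximum.

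**What to change.** Amend Table 1 and its synopsis copy together:

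- Make each possible result fall in exactly one column, or state an order of precedence. Print how the rows of each column are joined.
- Have the sponsor and the SMG resolve the 3/6 ACT cell, the cells shared by de-escalate and stop-study, and the single-SAE cell before further cohort data are reviewed, and record the resolution in the SMG charter. Which action belongs in each cell is a clinical decision on which this review takes no position.
- State that the SAE thresholds count patients.
- Use one cohort size throughout, or give the integer count for each permitted size in place of sixths.
- Make the N columns of the synopsis table and Table 3, the stated maximum and the number screened agree: either 6 per cohort, 18 in total and 30 screened, or a maximum of 20 and 34 screened.

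The cost is a protocol amendment touching Table 1, the synopsis, Table 3 and Section 14.1. It needs no new data; the stated maximum rises by 2 only if the larger third cohort is kept.
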